side effects, with headache being the most common complaint²⁸. The most serious adverse event is a seizure; however, using the safety parameters, it is an extremely rare event, with few reports of cases in the literature²⁹. Additionally, the risk of drug interaction observed with the use of antidepressants and other medications of continuous use is null, a situation very common among depressed elderly people. Also, rTMS does not negatively interfere with patients' cognitive function, and may even improve it in some aspects³⁰. Theta burst stimulation (TBS) is a method of rTMS that more closely mimics the natural rhythms of activity in the neurons of the brain and uses short bursts of stimulation at high frequencies, with the bursts themselves being applied 5 times per second³¹. Its main advantage against conventional rTMS is the shorter time of section (3 to 12 minutes, against 20-30). One non inferiority trial showed the same efficacy of the conventional rTMS³². No controlled studies with TBS have been performed in the treatment of geriatric depression; however, recent studies with the method have shown good prospects for the treatment of major depression in adults with meta-analyses demonstrating a possible clinical superiority over conventional rTMS³³⁻³⁸. In addition, the session time in which the patient stays in the machine during TBS is much shorter, which facilitates patient compliance.

We want to evaluate if TBS is a therapeutically effective alternative, and also with few side effects, for this geriatric population with depression. This may bring short-term clinical gains for depressed elderly patients who do not tolerate antidepressants or have been refractory to antidepressants.

Methods/design

Design and population

The study will be a randomized, double-blind, sham-controlled clinical trial in which volunteers will be recruited at the Clinical Hospital of the Medical School of University of São Paulo. They will be allocated to one of the groups: active TBS or sham stimulation. Participants will receive 20 consecutive work days of TBS and will return at the end of 4, 6, 8 and 12 weeks for one single session, evaluation of clinical outcomes. Those who do not present clinical improvement and have been allocated to the sham group may choose to receive 20 days of active stimulation after the end of the trial.

Randomization and allocation of participants

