The coil will be positioned in the prefrontal dorsolateral cortex, with intermittent TBS (TBSi) mode on the left and continuous TBS (TBSc) on the right (F3 and F4 positions determined by the 10–20 Electroencephalographic International System). 1800 pulses will be used on each side, totaling 11 minutes 39 seconds of total duration. TBS will have the following parameters: in cTBS bursts of three pulses at 50 Hz (20-ms interval between stimuli) will be applied continuously for 120 s total in the right DLPFC and iTBS bursts of three pulses at 50 Hz (20-ms interval between stimuli) will be applied for 2-s duration repeated every 10 s for a total time of 570 s also totaling 1800 pulses in the left DLPFC, both with 120% of motor threshold. We will use a magnetic stimulator device (MagVenture©) in study mode for double-blind trials. The coil has a side that is active and the other is sham. The applicant of TMS will be blinded too (after placing the coil over the patient's head and entering his number, the device tells if the position is correct or if you have to turn it, but the applicant does not know externally what is the sham side of the coil). The sham produces the same sound as the real one. We also put on the head electrodes that give stimulus to mimic the real magnetic coil (both groups receive this). There will be

20 consecutive sessions, one per day, except on weekends and holidays, totaling around 4 weeks. A day of stimulation with the same technique will be done in the 6th week, 8th week and 12th week.

Clinical variables

We will use the MINI questionnaire for the diagnosis of psychiatric disorders, applied by an experienced psychiatrist. It is translated and validated into the Portuguese language³⁹. The demographic and clinical profile of the patients will be evaluated by: gender, age, schooling, socioeconomic status, clinical comorbidities, use and dose of antidepressants and other psychoactive drugs.

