The main outcome will be measured using the HDRS scale. The primary evaluation will be done at the end of 6 weeks from the start of the first day of TBS. As secondary outcomes we will use the GDS (Geriatric Depression Scale), Cumulative Illness Rating Scale (CIRS), the global clinical impression scale (CGI), Positive and Negative Affect Scale (PANAS), Montgomery-Asberg Depression Rating Scale (MADRS), and Edinburgh Handedness Inventory (EHI). All scales have already been translated and validated into Portuguese⁴⁰. Outcomes will be measured on 7 occasions: baseline after 1, 2, 4, 6, 8 and 12 weeks of study entry. The presence of adverse effects and the Young mania (YMRS) questionnaire will also be evaluated to detect manic and / or hypomanic cycling.

Cognitive Assessments

The cognitive battery will be applied by experienced neuropsychologists. For cognitive assessments they will be exploratory, secondary outcomes will be measured on the baseline, on the 20th day of the session and the addenbrooke cognitive examination will also be reapplied on the 12th week. We will use the Addenbrooke's Cognitive Examination - Revised Version (ACE-R), Ravlt - Word List, Rey's complex figure, Stroop Test (violet version); Wais III - Subtest Codes; Trail Making A and B and WASI - Vocabulary and Matrix Reasoning subtest.

Biomarkers

BDNF (brain-derived neurotrophic factor) is implicated in the pathophysiology of depression. Recent meta-analyses have shown that depressed patients have lower serum levels of BDNF than normal subjects^{41,42}. The samples will be collected in dry tubes, centrifuged within two hours after collection, then separate the serum and refrigerate it in eppendorfs at -70oC in liquid nitrogen. The samples will therefore be stored in a cryogenic bank. They will be collected at the beginning of the study and in the 6th week.

Cerebrospinal fluid (CSF) samples will be collected by means of a lumbar puncture during the evaluation procedures before the intervention begins. They will be used for the investigation of beta-amyloid peptide (Aβ1-42) and Tau protein (total and phosphorylated). These determinations will allow

the analysis of the interaction between the presence of Alzheimer's disease pathology and the therapeutic response to the TBS intervention.

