Actigraphy consists of a wrist device equipped with an accelerometer, a microprocessor and an internal memory, which are capable of detecting and storing the movement record. It is used in the evaluation of sleep disorders such as diseases of circadian rhythm, insomnia and excessive daytime sleepiness. We will use the actigraphy on the left wrist of the volunteers 1 week before the beginning of the research and for another 4 weeks after the study. The objective is to assess sleep changes associated with the clinical response to magnetic stimulation.

Pupil Examination (PLR) the participant will do a test lasting about 20 minutes in which a camera phone will record the size of your pupil during this period while you will hear some sounds. The exam is painless and without side effects.

Sample size calculation:

Based on the clinical trial of Li⁴³, which demonstrated an efficacy favoring bilateral TBS in depression of 52.5% for the active group and 17.4% for the sham group, for a two-tailed p 0.05 and a power of 90%, the total sample size is 86 subjects. Considering a rate of friction of approximately 25%, we estimated the final sample size in 108 patients.

Statistical analysis

Statistical analysis will be performed with the Stata 16 SE program for Mac OS X. All analyzes will be made on the intention to treat principle (ie the data of all participants will be included in the analysis) in which lost data will be allocated according to the last observation carried forward principle and/or mixed data. Analyzes will be considered significant at p <0.05. We will use parametric tests to analyze the main outcomes, which are allowed by the sample size. Number of previous admissions, presence of clinical comorbidities, refractoriness (measured by the Massachusetts General Hospital scale - MGH-S)⁴⁴ will be analyzed as ordinal data. For the main outcome we will use a repeated measures analysis, having HDRS scores as Dependent variable and TBS as independent variable at week 8. Secondary analyses of the other scales and biomarkers will be performed in the same way, replacing HDRS as a dependent variable.

Study Flow Chart

We show below the flowchart for each patient throughout the study. It is worth remembering that TBS will be applied 23 times: 20 consecutive sessions (week 0 through week 4), 6th week, 8th week and 12th week. Still, patients who receive *sham* stimulation and who are still depressed may receive active stimulation at the end of the study.

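### Actigraphy is worded to run four weeks after the study, which literally records none of the randomised daily stimulation and may overlap active treatment of sham patients

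*Combined protocol and SAP*

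**What the plan says.** The actigraphy paragraph, at the end of the Biomarkers section, gives the recording period as "1 week before the beginning of the research and for another 4 weeks after the study" and the purpose as follows: "The objective is to assess sleep changes associated with the clinical response to magnetic stimulation".

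The rest of the timeline comes from other sections. Interventions describes "20 consecutive sessions, one per day, except on weekends and holidays, totaling around 4 weeks", and adds: "A day of stimulation with the same technique will be done in the 6th week, 8th week and 12th week". Clinical variables places the outcome assessments at "baseline after 1, 2, 4, 6, 8 and 12 weeks of study entry", so the last is at week 12. Design and population says that sham patients without clinical improvement "may choose to receive 20 days of active stimulation after the end of the trial". Study Flow Chart and Ethical aspects and safety repeat that offer at the end of the study, without a start date. Blinding keeps patients and evaluators unaware of allocation until the study ends.

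Table 1 has no actigraphy row, and no other section states when the device is worn.

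**The concern.** A measure meant to track sleep alongside response to stimulation should be recorded while randomised stimulation is being given, or at least while the two arms still differ only by their allocation. Read literally, the second window does neither. It opens after the last assessment, outside the period for which blinding is promised. It also falls where part of the sham arm, selected for not having improved, may be receiving active stimulation.

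If the text is followed as it stands, the trial would hold no sleep recording from the daily course, and that recording cannot be recovered later. In an analysis by allocated arm, patients recorded during active stimulation would still count as sham. The stake is limited: actigraphy is ancillary and is not named among the secondary outcomes in the abstract, Clinical variables or the Discussion.

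**Working it through.** The plan gives no figure to reproduce. The check is timeline arithmetic, with week 0 as the first session.

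**Inputs**
- Daily course (Interventions): 20 sessions on work days. 20 / 5 per week = 4 weeks, which agrees with the plan's own approximate length. This is weeks 0 to 4.
- Single sessions (Interventions): weeks 6, 8 and 12.
- Last assessment (Clinical variables, Table 1): week 12, taken as the end of the study.
- Actigraphy (Biomarkers): 1 week before, 4 weeks after; 1 + 4 = 5 recording weeks.
- Optional active course for unimproved sham patients (Design and population): 20 days. Assuming the same work-day pattern, 20 / 5 = 4 weeks. Start not stated.

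**Readings of the second window**

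| Reading | Second window | Daily-session weeks recorded | Overlap with the optional active course |
|---|---|---|---|
| A. After the study ends (literal) | weeks 12 to 16 | 0 of 4 | 0 to 4 weeks |
| B. From study start | weeks 0 to 4 | 4 of 4 | none |
| C. After the 20-session course | weeks 4 to 8 | 0 of 4 | none |

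**Overlap under reading A.** Let d be the delay in weeks from week 12 to the start of the active course. The recording runs over weeks 12 to 16 and the course over weeks 12 + d to 16 + d, so the overlap is max(0, 4 − d) weeks:
- d = 0: 4 weeks
- d = 2: 2 weeks
- d = 4 or more: 0 weeks

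The documents do not give d, so the whole range from 0 to 4 stays open. They also give no uptake for the offer, so the share of the sham arm affected cannot be calculated.

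**Does another passage settle it?** Other procedures are tied to study weeks: the pain tests to a time before the sessions and to week 4, the blood samples to the start and week 6. Actigraphy is not. Three readings give three different data sets, and the text does not choose between them.

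**The case against.** The best defence is that reading B was intended. The phrase follows a one-week lead-in with a further four weeks, which sounds like continued wear. Four weeks is exactly the length of the daily course, and the stated objective fits wear during stimulation. The protocol also uses the word *after* loosely: the abstract puts the main comparison six weeks after the intervention, whereas Clinical variables says "The primary evaluation will be done at the end of 6 weeks from the start of the first day of TBS". On reading B all four daily-session weeks are recorded and nothing overlaps the post-trial course. This stands as a plausible account of intent. It does not remove the defect, because the sentence as written says something else and staff would have to guess.

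The missing row in Table 1 proves little by itself. The table also leaves out cortical excitability, sensory testing, pain modulation and the pupil examination, so the omission is no evidence for the literal reading. It only means that the table does not correct the wording.

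A reader might infer that the sham arm will be contaminated and the sleep comparison biased toward no difference. The documents do not establish this. The active course is optional, limited to sham patients who have not improved, and without a start date. The direction of any bias would also depend on active stimulation changing sleep in the expected way.

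**Conclusion.** The point holds as a defect of wording with a real consequence if followed. Taken literally, actigraphy records none of the 4 weeks of randomised daily stimulation, and its second window may overlap active stimulation in some sham patients by 0 to 4 weeks. This rests on the study ending at week 12 and on the optional course keeping the work-day pattern. If reading B was meant, neither problem arises and only the text is wrong.

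A reader might go further and conclude that actigraphy cannot meet its objective. That is too strong. Even with recording at weeks 12 to 16, the change from the week before treatment could be related to clinical response in the active arm and in sham patients who take no active course. The assessment would be weaker and possibly confounded, not impossible. Nor should the lack of recording at the week 6 primary visit be held against the plan here: a window over the daily sessions would not cover week 6 either.

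No conclusion on the HDRS or on a named secondary outcome is affected. This is a minor correction, worth making before recording starts.

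**What to change.** Replace the phrase with a window in study weeks that lies inside the blinded randomised period, for example the week before the first session and weeks 1 to 4 of daily sessions. Add an actigraphy row to Table 1 at Baseline and weeks 1 to 4. The sponsor should confirm that this matches the intent.

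If any recording after week 12 is kept, state that data recorded once a sham patient starts active stimulation are excluded from the randomised sleep comparison, and record that start date. Such an exclusion removes data only from sham patients who did not improve, so what remains is a selected group. This is a further reason to prefer the window during the daily sessions.

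The cost is one phrase and one table row. Recording stays at five weeks per patient (1 + 4). Keeping recording after week 12 would add one sentence to Statistical analysis.

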Background: Recurrent transcranial magnetic stimulation (rTMS) is a consolidated procedure for the treatment of depression, with several meta-analyses demonstrating its efficacy. The theta burst stimulation (TBS) method is a modification of the usual rTMS protocol, with short bursts of stimulation at high frequencies, with the bursts themselves being applied 5 times per second. As a new intervention method, there are still few studies evaluating its efficacy in treatment of major depression. However, a recently published meta-analysis has pointed to benefits of this therapeutic modality. To date, there are no studies published with this method for the treatment of geriatric depression.

Methods/design: The proposed study is designed as a double-blind clinical trial to assess the efficacy of rTMS theta-burst in the treatment of major depressive disorder in the elderly, in a sample of 108 individuals. Patients will be randomized to two groups: the experimental (TBS) and comparative (sham) group. Inclusion criteria include a diagnosis of Major Depressive Episode and a minimum age of 60 years. The coil will be positioned in the dorsolateral prefrontal cortex, with intermittent TBS mode on the left and continuous TBS on the right. There will be 20 consecutive sessions. Outcome measures will be at eight occasions: before the intervention (baseline) and after 1, 2, 4, 6, 8 and 12 weeks of onset. The main clinical result will be measured using the Hamilton Depression Scale (HDRS), comparing the initial scores with those obtained at the end of 6 weeks after the intervention. As secondary outcomes, we will use the Global Clinical Impression Scale (CGI), the CIRS (Cumulative Disease Assessment Scale), the Geriatric Depression Scale (GDS), the intermediate scores obtained on the HDRS scale and the variations in serum BDNF concentrations. As parameters of tolerability and safety, the incidence of adverse events and the occurrence of manic and / or hypomanic symptoms will also be assessed by the Young Mania Scale (YMRS).

EXPECTED RESULTS: TBS stimulation will prove to be a safe, well-tolerated and effective intervention for the treatment of major depression in the elderly, becoming a more therapeutic option, particularly useful for patients with poor response or contraindications to the use of antidepressants.

Trial registration: NCT0484292 Registered on <https://clinicaltrials.gov/ct2/show/NCT04842929>

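### The attrition allowance does not work out: 108 patients less 25% leaves 81, not the 86 the plan requires

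*Combined protocol and SAP*

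**What the plan says.** The section headed Sample size calculation takes response rates from an earlier bilateral TBS trial: "52.5% for the active group and 17.4% for the sham group". The error rate and power are set by "for a two-tailed p 0.05 and a power of 90" per cent, and the result is that "the total sample size is 86 subjects". The attrition step comes next: "Considering a rate of friction of approximately 25%, we estimated the final sample size in 108 patients". The abstract (Methods/design) repeats the final figure, "in a sample of 108 individuals", and describes two groups without an allocation ratio. No inflation formula is shown.

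The Statistical analysis section, which follows directly, plans an intention-to-treat analysis of all participants. Missing values are to be filled by last observation carried forward and/or what the plan calls mixed data.

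**The concern.** An attrition allowance exists so that, after the expected losses, the required number is still there. A reader can test that by hand: take 25% off 108 and see whether 86 remain. They do not. The pattern suggests that 25% of the required number was added, whereas losses are taken from the larger enrolled number.

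What is at stake is the reliability of a stated figure rather than the viability of the trial. The sentence implies protection against 25% loss that 108 does not give. If attrition does reach the assumed level, the trial will report 81 completers against its own published requirement of 86, with nothing in the plan to explain the gap.

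**Working it through.** **Inputs** (all from Sample size calculation, except the ratio)

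- Response rates: p1 = 0.525 (active), p2 = 0.174 (sham); difference d = 0.351
- Two-sided alpha 0.05 (z = 1.960); power 90% (z = 1.282)
- Required total 86; attrition about 25%; final size 108
- Allocation 1:1 (assumed; the documents give two groups but no ratio)

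**Step 1. Reproduce the 86.** With p̄ = (0.525 + 0.174)/2 = 0.3495, the uncorrected size per arm is

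n = [1.960 × √(2 p̄(1 − p̄)) + 1.282 × √(p1(1 − p1) + p2(1 − p2))]² / d² = 36.66, so 37 per arm and 74 in total.

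With the continuity correction,

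n_c = (n/4) × [1 + √(1 + 4/(n d))]² = 42.16, so 43 per arm and **86 in total**.

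This matches the plan exactly. At the same alpha and power, the unpooled formula gives 68 and the arcsine formula 74; neither matches. The base figure is therefore sound on the plan's inputs, and the discrepancy lies in the attrition step alone.

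**Step 2. Reproduce the 108.**

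- Multiplying: 86 × 1.25 = 107.5, rounded up to **108**. This matches the plan.
- Dividing: 86 / (1 − 0.25) = 114.7, rounded up to **115** (116 for equal arms). This does not match.

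**Step 3. What 108 delivers.**

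- Remaining after 25% loss: 108 × 0.75 = **81**, which is 86 − 81 = 5 short (5/86 = 5.8%).
- Largest loss that still leaves 86: 1 − 86/108 = **20.4%**.
- Gap in enrolment: 115 − 108 = 7, or 116 − 108 = 8 for equal arms.

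**Step 4. Power at the number remaining.** Inverting the continuity-corrected calculation, with n per arm,

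power = Φ{[d − 1/n − 1.960 × √(2 p̄(1 − p̄)/n)] / √([p1(1 − p1) + p2(1 − p2)]/n)}

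| Method | At 81 | At 86 |
|---|---|---|
| Continuity-corrected (the method that gives 86) | 88.6% | 90.7% |
| Uncorrected | 92.7% | 94.1% |
| Fisher exact | 90.5% (41 + 40) | 91.5% (43 + 43) |

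Fisher power at 40 + 40 is 88.5%.

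**The case against.** The strongest objection is that nobody leaves the analysis. The plan analyses all participants, so the analysis set is 108 and the 81 describes only those with complete data. On the formula that gives 86, nominal power at 108 is 96.3%. That is an upper bound, since carried-forward values can dilute the effect, but it shows that 25% attrition need not by itself take power below 90%. This stands as a caution about what 81 means. It does not mend the sentence: the plan chose to inflate 86 for losses, and the allowance it chose does not restore 86.

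Second, the cost depends on the method. Even among 81 completers, power falls below 90% by the continuity-corrected formula but not by the uncorrected one, and Fisher's test lies on either side of 90% depending on how the patients split. This also stands: the shortfall is about 1.4 points below 90% on the plan's own method and may be nil on another. Moreover, the planned primary analysis is a repeated-measures comparison of HDRS scores, so every power figure here describes the two-proportion sizing calculation and not the primary test.

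Third, the plan says only approximately 25%. That does not stretch to 20.4%, and the exact match with 86 × 1.25 makes the multiplication the likely source. It is possible that 20% was meant, since 86 / 0.80 is also 107.5. The printed rate would then be the error, and the sentence would still need correcting.

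**Conclusion.** The concern holds. A requirement of 86 evaluable patients, 25% attrition and 108 enrolled are mutually inconsistent: 108 leaves 81 at that rate, and keeping 86 would take 115 or 116. The arithmetic uses only the plan's three figures; equal arms matter only for the choice between 115 and 116.

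The consequence for power is small. Under 1:1 allocation and the continuity correction, both inferred from the exact reproduction of 86, it drops by about two points (90.7% to 88.6%). This should not be read as a claim that the trial is materially underpowered. It is a figure that is wrong as written and that any reader can check.

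**What to change.** Keep 108 and correct the attrition sentence in Sample size calculation in one of two ways:

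- 108 randomised allows for 20% attrition and leaves 86 patients with complete data; or
- 108 randomised with 25% attrition leaves 81 patients with complete data, with about 88–89% power under the response rates and two-proportion method used for sizing.

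The documents give no basis for either rate, so the choice should follow the attrition the sponsor actually expects, not the rate that happens to fit 108. Either version should show the inflation formula and say that the number refers to patients with complete data while the primary analysis includes everyone randomised.

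The cost is one corrected sentence and a stated figure that becomes slightly less favourable. Enrolment, design and analysis are unchanged, and the abstract's 108 can stay.

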Table 1. Study schedule

	Triage	Baseline	Week						
			1	2	3	4	6	8	12
Assessment of eligibility	X								
Structured interview (MINI)	X								
Consent form	X								
Theta-burst stimulation (active/sham)			D	D	D	D	W	W	W
Clinical interviews	X		X	X		X	X	X	X
Adverse effects			X	X		X	X	X	X
Blood collection for serum biomarkers		X					X		
Neuropsychological evaluation		X					X		X
Cerebrospinal fluid collection		X							

“D” and “W” represent interventions performed daily and weekly, respectively.

Ethical aspects and safety

The rTMS is very safe when used properly and has few adverse effects, and as mentioned above, the most common is headache. Applications will always be made in a hospital setting with a physician present. We will evaluate patients 23 times over 12 weeks - so that we can quickly identify any worsening of the clinical picture and perform early intervention.

The study is approved by the Research Ethics Committee (CAAE: 80215117.5.0000.0068). All enrolled subjects will consent to participate through an Informed Consent Form. All the procedures described present minimal risk. If a volunteer presents a risk of major suicide, the same will be excluded from the study, adopting the standard procedure for the management of this type of patient. Participants may have access to their data and may leave the study at any time, without prejudice to any treatment they may perform within the institution. The data will be collected, analyzed and published in order to preserve the anonymity of the individual. In addition, the study will be conducted in accordance with all requirements of the Research Ethics Committee and also based on the recommendations established in the Declaration of Helsinki (1964), as amended in Tokyo (1975), Venice (1983) and Hong Kong (1989). As a benefit, participants will be able to participate in a clinical trial to treat their clinical condition. This

will be possible even if they receive sham stimulation, as they may receive active stimulation at the end of the study if they still have severe depressive symptoms.

Discussion

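### With about 25% attrition expected, the plan does not say whether LOCF or a mixed model decides the primary HDRS result; if LOCF decides, a real effect can be understated

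*Combined protocol and SAP*

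**What the plan says.** The Statistical analysis section commits to intention to treat for all analyses and then states that "lost data will be allocated according to the last observation carried forward principle and/or mixed data". LOCF alone, the mixed option alone, or both would comply. No section ranks them, labels one as a sensitivity analysis, or states a missing-data assumption.

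The main analysis is described only as a repeated measures analysis, "having HDRS scores as Dependent variable and TBS as independent variable at week 8". The type of model is not given.

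The expected loss is in Sample size calculation: "Considering a rate of friction of approximately 25" percent, tied to no visit. Interventions describes "20 consecutive sessions, one per day, except on weekends and holidays, totaling around 4 weeks", and Clinical variables gives the assessments: "Outcomes will be measured on 7 occasions: baseline after 1, 2, 4, 6, 8 and 12 weeks of study entry".

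The primary visit is itself unsettled. The abstract refers to "comparing the initial scores with those obtained at the end of 6 weeks after the intervention" and Clinical variables says "The primary evaluation will be done at the end of 6 weeks from the start of the first day of TBS", whereas the analysis section names week 8.

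**The concern.** Under LOCF, a patient last seen at week 1 or 2 enters the primary comparison with a score taken partway through daily stimulation. If improvement or separation of the arms was incomplete at that point, the carried score is not the primary-visit value. Three consequences follow.

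- **Equal loss in both arms.** The treatment difference shrinks towards zero. Type I error stays near 5%, but the estimate is biased.
- **Unequal loss.** Patients in both arms may improve over time, so the arm that loses more patients looks worse. The bias can go either way and type I error can rise. The documents neither state nor exclude unequal loss.
- **Method left open.** If both analyses are run and the deciding one is chosen afterwards, the overall false-positive rate exceeds 5% even with equal loss.

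**Working it through.** **The plan's own figures.** Inputs from Sample size calculation: response 52.5% versus 17.4%, two-sided 0.05, power 90%. Equal allocation is assumed.

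- Mean proportion 0.3495; difference 0.351.
- Uncorrected n per arm = [1.96·√(2·0.3495·0.6505) + 1.2816·√(0.525·0.475 + 0.174·0.826)]² / 0.351² = (1.3216 + 0.8035)² / 0.1232 = 36.7.
- With continuity correction: (36.7/4)·[1 + √(1 + 4/(36.7·0.351))]² = 42.2, so 43 per arm and 86 in total, as stated.
- 86 × 1.25 = 107.5, rounded to 108, as stated. This covers a loss of 1 − 86/108 = 20.4%. At 25% loss, 81 remain.

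This sizing uses response rates and supplies no HDRS difference or SD. Everything below therefore rests on assumed HDRS inputs.

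**Hand calculation, equal loss.** Let a share q leave before the primary visit, carrying a fraction f of the final effect. LOCF then keeps 1 − q(1 − f) of the true difference.

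| q | f | Share kept | True 4 points becomes |
|---|---|---|---|
| 25% | 0 | 75% | 3.0 |
| 25% | 0.5 | 87.5% | 3.5 |
| 25% | 1 | 100% | 4.0 |
| 13% | 0 | 87% | 3.5 |

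As a power illustration, take a standardised difference of 0.699, which gives 90% power at 43 per arm. At 54 per arm, power is Φ(0.699·k·√27 − 1.96), where k is the share kept: 95% for k = 1, 89% for 0.875 and 78% for 0.75.

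**Hand calculation, unequal loss.** Let sham improve by C and the true difference be D, with loss at random within arm. The LOCF difference is D[1 − q_TBS(1 − f)] − C(q_TBS − q_sham)(1 − f). With D = 0, C = 8, f = 0.5, and 15% lost in TBS against 35% in sham, this is 8·0.20·0.5 = 0.8 points in favour of TBS where no effect exists. With D = 4 and the losses reversed, it is 4·0.825 − 0.8 = 2.5.

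**Simulation.** There were 54 patients per arm and 20,000 replicates per scenario. Assumed: baseline HDRS mean 22 and SD 4, with SD rising to 7 by week 6; true difference 0 or 4. The 48 settings cross:

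- sham improvement of 4 or 8 points;
- linear, week-4-plateau or early improvement;
- adjacent-visit correlation 0.6 or 0.8;
- early or late dropout;
- primary visit at week 6 or 8.

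Dropout depends on the last observed score. LOCF with baseline-adjusted ANCOVA is compared with a maximum-likelihood mixed model (arm by visit, baseline by visit, unstructured covariance). Ranges are minimum to maximum over settings.

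| Scenario | LOCF | Mixed model |
|---|---|---|
| Equal 25%, true 4: estimate | 3.1–3.7 | 4.0 |
| Equal 25%, true 4: power | 54–83% | 70–82% |
| Equal 25%, no effect: type I error | 4.7–5.6% | 4.4–5.2% |
| 13% per arm by the primary visit, true 4 | 3.5–3.8 | not reported |
| Same score-dependent rule in both arms (22–24% TBS, 25–28% sham), true 4 | 3.2–3.9 | 4.0 |
| 20% vs 30%, no effect: type I error | 5.0–9.1% | not reported |
| 15% vs 35%, no effect: type I error | 6–21% | not reported |
| 35% lost in sham, true 4 | 4.1–5.1 | not reported |
| 35% lost in TBS, true 4 | 1.1–3.2 | not reported |

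At equal 25% loss with a true 4 points, the mixed model had more power in 41 of 48 settings (difference −6 to +18 percentage points, median +5). The LOCF standard error was calibrated (mean SE over empirical SD 0.98–1.01 with no effect), so the fault is bias.

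**Choosing between the methods.** At equal 25% loss and no effect, at least one of the two tests gives p < 0.05 in 5.9–7.3% of trials (median 6.5%). With a true 4 points they disagree on significance in 6–23%.

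**Dropout driven by the unobserved current score** (24 settings, week 6). With 15% vs 35% lost and no effect, LOCF is off by 0.1–1.3 points with type I error 5.2–17.7%; the mixed model is off by 0.2–0.5 with 4.7–5.9%. With a true 4 points:

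| Loss | LOCF | Mixed model |
|---|---|---|
| Equal 25% | 3.08–3.63 | 3.96–4.00 |
| 35% in sham | 3.90–4.81 | 3.51–3.80 |
| 35% in TBS | 1.39–3.30 | 4.18–4.43 |

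**The case against.** The strongest reply is that a repeated measures analysis, in the same paragraph as the mixed option, naturally reads as a mixed model, so no LOCF bias would arise. That reading is possible. It does not settle the point: such an analysis can be run on LOCF-filled data, and the paragraph expressly permits LOCF for every analysis.

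Other objections carry some weight.

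- **Timing of loss.** The 25% is not tied to a visit and follow-up runs to week 12, so placing all of it before the primary visit is the heavier case. At 13% the bias is modest.
- **Inputs and tests.** The HDRS inputs are assumed, and the plan mentions no baseline adjustment. The power and disagreement figures therefore belong to the two analyses simulated and are not properties of this trial. The attenuation of the visit contrast does carry over.
- **Direction.** LOCF can overstate as well as understate, and at 20% vs 30% loss the rise in type I error is negligible in the mildest settings.
- **The mixed model is not exact either.** Its near-perfect 4.0 depends on missingness being explained by observed scores. With outcome-driven loss concentrated in sham, it understated the effect in every setting and LOCF could be closer to the truth.
- **Suicide-risk removal.** "If a volunteer presents a risk of major suicide, the same will be excluded from the study" may link loss to outcome, but the sentence does not say whether it applies after randomisation.

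These limit the size of the problem. None of them identifies a deciding method.

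**Conclusion.** The concern holds. The method that decides the primary result is left open, and one permitted option gives a biased contrast whenever patients leave before the arms have fully separated. If LOCF decides and 25% leave each arm before the primary visit, a true 4 points is reported about 0.3 to 0.9 points too small under the assumptions above. At 13% the shortfall is 0.2 to 0.5. Larger errors, and inflated type I error, need unequal loss, which is hypothetical here. The cost of choosing between methods is smaller but needs no unequal loss.

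Confidence in the size is medium, because SD, trajectory, correlation and dropout timing are all assumed. That no method is named rests on the text alone. This is a cheap improvement and does not threaten the design.

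**What to change.** Delete the wording that leaves LOCF as an alternative and name one primary analysis: a likelihood-based mixed model on all observed post-baseline HDRS scores, with arm, visit, arm by visit and baseline HDRS, a covariance structure stated in advance (unstructured is one reasonable choice), and no imputed values. State its missing-at-random assumption. Take the arm contrast at one prespecified visit, once the week 6 and week 8 statements have been reconciled. Keep LOCF at most as a labelled sensitivity analysis. One not-missing-at-random sensitivity analysis, such as delta-adjusted multiple imputation, is optional but useful, because the mixed model is not exact when loss depends on unobserved scores. Make the change before unblinding.

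The cost is a few sentences; the visits at weeks 1, 2, 4, 6, 8 and 12 are already planned. The standard error is somewhat larger: 1.3–1.6 points against 1.1–1.5 under LOCF in the simulation, or 8–25% larger at equal 25% loss with no true effect, because carried-forward scores are no longer counted as observed. In a minority of settings, those with late dropout and mostly with early or week-4-plateau improvement, LOCF had up to 6 percentage points more power.
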